5.7.2 Laboratory Tests

Hematological, serum biochemistry, adrenal laboratories, and urine data and their changes (only for continuous laboratory parameters) from baseline will be summarized by visit.

Shift tables for hematology and biochemistry data will also be presented showing change in CTCAE severity grade from baseline to each visit. For parameters for which a CTCAE scale does not exist, shift tables will be presented showing change in results from baseline (normal, low and high [or abnormal]) to each visit (normal, low and high [or abnormal]).

Summary of abnormalities in laboratory variables pre-defined for safety monitoring will be done per the following Table 2.

Table 2: Safety Monitoring Parameters and Actions to be Taken

Organ System and Laboratory Parameter	Stop Study Drug Immediately, Confirm Abnormal Value, and Then Start Work-Up	Stop Study Drug After Confirming ^a Abnormal Value, and Then Start Work-Up	Continue Study Drug, Confirm Abnormal Value, and then Start Work-Up ^a
Hepatic			
Serum total bilirubin	\geq Grade 3 ($\geq 3.0 \times$ ULN)	Grade 2 (1.5 – 3.0 x ULN)	---
Serum GGT	\geq Grade 3 ($\geq 5.0 \times$ ULN)	Grade 2 ($>2.5 - 5.0 \times$ ULN)	---
Serum ALT			\uparrow of >150 U/L with stable or \downarrow CK
Adrenal			
Plasma ACTH	---	$>$ ULN (and plasma cortisol $<$ LLN)	$>$ ULN (and cortisol WNL)
Renal			
Serum cystatin C	>2.00 mg/L	$>1.33 - 2.00$ mg/L	---
Serum creatinine	\geq Grade 2 ($\geq 1.5 \times$ ULN for age)	Grade 1 ($>$ ULN – $1.5 \times$ ULN for age)	---
Serum BUN	$\geq 3.0 \times$ ULN	$\geq 1.5 - 3.0 \times$ ULN	---
Urine protein: urine creatinine (spot)	---	>0.40 mg:mg	---
Urine protein: urine osmolality (spot)	---	>0.30 mg/L:mOsm/kg	---
Urine blood (by dipstick)	4+ (Large)	3+ (Moderate)	2+ (Small)

Organ System and Laboratory Parameter	Stop Study Drug Immediately, Confirm Abnormal Value, and Then Start Work-Up	Stop Study Drug After Confirming ^a Abnormal Value, and Then Start Work-Up	Continue Study Drug, Confirm Abnormal Value, and then Start Work-Up ^a
Serum electrolytes	Grade 3-4	Grade 2	Grade 1
Serum Na ⁺ , high	>155 mmol/L	>150 – 155 mmol/L	---
Serum Na ⁺ , low	<130 mmol/L	---	---
Serum K ⁺ , high	>6.0 mmol/L	>5.5 – 6.0 mmol/L	---
Serum K ⁺ , low	<3.0 mmol/L	---	---
Serum Mg ²⁺ , high	>1.23 mmol/L	---	---
Serum Mg ²⁺ , low	<0.4 mmol/L	<0.5 – 0.4 mmol/L	---
Total serum Ca ²⁺ , high	>3.1 mmol/L	>2.9 – 3.1 mmol/L	---
Total serum Ca ²⁺ , low	<1.75 mmol/L	<2.0 – 1.75 mmol/L	---
Serum phosphorous	<0.6 mmol/L	<0.8 – 0.6 mmol/L	---
Serum HCO ₃ ⁻	<11 mmol/L	<16 – 11 mmol/L	---

^a Laboratory abnormalities may be confirmed immediately or at the next scheduled clinic visit based on investigator judgment.

Abbreviations: ACTH = adrenocorticotrophic hormone, ALT = alanine aminotransferase, BUN = blood urea nitrogen, Ca²⁺ = calcium, CK = creatine kinase, GGT = gamma glutamyl transferase, HCO₃⁻ = bicarbonate, K⁺ = potassium, Mg²⁺ = magnesium, Na⁺ = sodium, ULN = upper limit of normal, WNL = within normal limits

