10.4.5.2. Laboratory Data

Hematological, serum biochemistry, adrenal laboratories, and urine data and their changes (only for continuous laboratory parameters) from baseline will be summarized by visit. Hematological, serum biochemistry, adrenal laboratories, and urine data will be graded according to CTCAE severity grade when applicable. For parameters for which a CTCAE scale does not exist, the frequency of patients with values below, within, and above the normal ranges will be summarized. Summary tables will be presented for each relevant assay to show the number of patients by severity grade with corresponding percentages. Subjects will be characterized only once for a given assay, based on their worst severity grade observed during the time period of interest.

Shift tables for hematology, serum biochemistry, adrenal laboratories, and urine data will also be presented showing change in CTCAE severity grade from baseline to each visit. For parameters for which a CTCAE scale does not exist, shift tables will be presented showing change in results from baseline (normal, low and high [or abnormal]) to each visit (normal, low and high [or abnormal]).

Separate listings and tables will be created for parameters for assessment of adrenal, hepatic, and renal monitoring based on the conditions listed in Section 6.3.

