3.3 Study Endpoints

Primary:

- Safety profile characterized by type, frequency, severity, timing, and relationship to ataluren of any adverse events or laboratory abnormalities

Secondary:

- In ambulatory subjects,
 - i. change from baseline in 6MWD as measured by the 6-minute walk test (6MWT)
 - ii. change from baseline in physical function as measured by the North Star Ambulatory Assessment (NSAA)
 - iii. change from baseline in timed function tests (time to stand from supine and time to run/walk 10 meters)
- In non-ambulatory subjects,
 - i. change from baseline in pulmonary function test - % predicated forced vital capacity (FVC) and % predicted forced expiratory volume in 1 second (FEV1) as measured by spirometry
 - ii. change from baseline in patient and parent/caregiver-reported activities of daily living, as measured by the Egen Klassifikation (EK) scale

- All subjects,
 - i. changes in patient and/or parent/caregiver reports of disease status as measured by a standardized survey administered by site personnel

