5 STATISTICAL ANALYSIS

5.1 General Statistical Considerations

Summary tables for continuous variables will contain the following statistics: n, mean, standard deviation, standard error, 95% confidence intervals (CIs) on the mean, median, minimum, and maximum. Summary tables for categorical variables will include N, n, and percentages. In by-visit summaries, the analysis visits will be derived via visit mapping windows.

By-patient listings will be created for each CRF module. The data will be listed by center/subject ID and visit.

In addition, all analyses will be performed by corticosteroid use (yes or no before or during the study), by ambulatory status (ambulatory or non-ambulatory) at baseline, and overall, unless specified otherwise.

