6 DATA HANDLING

6.1 Analysis Visits based on Visit Windows

Since some subjects had early terminations or unscheduled visits in during, the derived analysis visits will be generated by visit window defined as follows.

The derived visits will be generated by visit window defined as follows.

Let ADY=assessment date –first dose date +1.

```
IF .<= ADY <=1 THEN AVISIT= BASELINE AND AVISITN=1;
IF 42<= ADY <=126 THEN AVISIT=WEEK 12 AND AVISITN=2;
IF 126<ADY <=210 THEN AVISIT=WEEK 24 AND AVISITN=3;
IF 210<ADY <=294 THEN AVISIT=WEEK 36 AND AVISITN=4;
IF 294<ADY <=378 THEN AVISIT=WEEK 48 AND AVISITN=5;
IF 378<ADY <=462 THEN AVISIT=WEEK 60 AND AVISITN=6;
IF 462<ADY <=546 THEN AVISIT=WEEK 72 AND AVISITN=7;
IF 546<ADY <=630 THEN AVISIT=WEEK 84 AND AVISITN=8;
IF 630<ADY <=714 THEN AVISIT=WEEK 96 AND AVISITN=9;
IF 714<ADY <=798 THEN AVISIT=WEEK 108 AND AVISITN=10;
IF 798<ADY <=882 THEN AVISIT=WEEK 120 AND AVISITN=11;
IF 882<ADY <=966 THEN AVISIT=WEEK 132 AND AVISITN=12;
IF 966<ADY <=1050 THEN AVISIT=WEEK 144 AND AVISITN=13;
IF 1050<ADY <=1134 THEN AVISIT=WEEK 156 AND AVISITN=14;
IF 1134<ADY <=1218 THEN AVISIT=WEEK 168 AND AVISITN=15;
IF 1218<ADY <=1302 THEN AVISIT=WEEK 180 AND AVISITN=16;
IF 1302<ADY <=1386 THEN AVISIT=WEEK 192 AND AVISITN=17;
IF 1470<ADY <=1554 THEN AVISIT=WEEK 216 AND AVISITN=19;
IF 1554<ADY <=1638 THEN AVISIT=WEEK 228 AND AVISITN=20;
IF 1638<ADY <=1722 THEN AVISIT=WEEK 240 AND AVISITN=21
IF 1722<ADY <=1806 THEN AVISIT=WEEK 252 AND AVISITN=22
IF 1806<ADY <=1890 THEN AVISIT=WEEK 264 AND AVISITN=23
IF 1890<ADY <=1974 THEN AVISIT=WEEK 276 AND AVISITN=24
IF 1974<ADY <=2058 THEN AVISIT=WEEK 288 AND AVISITN=25
IF 2058<ADY <=2142 THEN AVISIT=WEEK 300 AND AVISITN=26
```

IF 2142<ADY <=2226 THEN AVISIT=WEEK 312 AND AVISITN=27

IF 2226<ADY <=2310 THEN AVISIT=WEEK 324 AND AVISITN=28

IF 2310<ADY <=2394 THEN AVISIT=WEEK 336 AND AVISITN=29.

If there are more than 1 valid assessment within one visit window, the last one will be chosen as the analysis value.

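### The SAP omits, undeclared, the protocol's worst-grade-per-patient laboratory table and its adrenal and urine shift tables, and the by-visit shift tables it keeps cannot replace them

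*SAP*

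**What the plan says.** The primary endpoint in SAP 3.3 is "Safety profile characterized by type, frequency, severity, timing, and relationship to ataluren of any adverse events or laboratory abnormalities". Laboratory frequency and severity are therefore primary material.

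Protocol 10.4.5.2 sets out how to report them. It asks for grade tables: "Summary tables will be presented for each relevant assay to show the number of patients by severity grade with corresponding percentages". It fixes the counting rule: "Subjects will be characterized only once for a given assay, based on their worst severity grade observed during the time period of interest". It also gives the scope of the shift tables: "Shift tables for hematology, serum biochemistry, adrenal laboratories, and urine data will also be presented". Separately, it asks for listings and tables of the adrenal, hepatic and renal monitoring parameters.

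SAP 5.7.2 plans by-visit summaries of all four laboratory groups and then shift tables: "Shift tables for hematology and biochemistry data will also be presented showing change in CTCAE severity grade from baseline to each visit". It adds a summary of abnormalities according to its Table 2 thresholds. It contains no table by worst grade. SAP 5.1 says how visits are formed: "In by-visit summaries, the analysis visits will be derived via visit mapping windows". SAP 6.1 gives the windows, for example "IF 294<ADY <=378 THEN AVISIT=WEEK 48 AND AVISITN=5", and the choice among several values: "If there are more than 1 valid assessment within one visit window, the last one will be chosen as the analysis value".

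SAP 7 lists two kinds of change from the protocol, the removal of paired t-tests and the addition of subgroups. It lists no laboratory change. SAP 1 says that the SAP prevails where the two documents conflict.

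**The concern.** The protocol's table answers the basic safety question: for a given assay, how many boys ever reached Grade 2, 3 or 4 on treatment? A set of visit-by-visit tables does not answer it, because the same boy may appear at many visits or different boys may appear at each. SAP 5.7.1 counts each subject once at highest severity for adverse events, so the principle is accepted there and missing here.

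The last-value rule adds a directional problem. Extra samples within a window are often repeats taken because the first value was abnormal. When the repeat is lower, the shift table shows the lower grade.

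At stake is whether the report of a study with a safety primary endpoint can state per-patient laboratory toxicity for every assay. Because the SAP prevails and SAP 7 is silent, a reader of the report would not know that a protocol table had been left out.

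**Working it through.** The plan states no figure for this point, so the check is a comparison of the two texts plus simple counting.

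**1. Protocol 10.4.5.2 against SAP 5.7.2**

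| Output | Protocol | SAP |
|---|---|---|
| Patients by worst grade, once per assay | Required | Absent |
| Shift tables, hematology and biochemistry | Required | Kept |
| Shift tables, adrenal and urine | Required | Not named |
| Monitoring-parameter tables | Required as a separate item | Kept (Table 2) |
| Departure listed in SAP 7 | n/a | No |

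The Table 2 summary is thus the counterpart of a different protocol item and does not substitute for the worst-grade table.

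**2. Window width.** Week 48 covers days 295 to 378: 378 − 294 = 84 days. The other printed windows are also 84 days wide, except Week 12 (126 − 42 + 1 = 85). The baseline rule ends at day 1 and the Week 12 rule starts at day 42, so a value on days 2 to 41 maps to no visit. The schedule has no laboratory visit there, so only unscheduled samples are affected.

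**3. When a value is overwritten.** Scheduled draws are 1 (screening) + 1 (Week 1) + 20 (every 12 weeks to Week 240) + 1 (post-treatment) = 23, which matches protocol Table 5. Usually one scheduled value falls in each window, so overwriting needs a second, later value.

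- *Repeat test.* A Grade 3 on day 337 and a Grade 0 repeat on day 351 both lie in the Week 48 window. The SAP rule shows Grade 0; the protocol's counting rule shows Grade 3.
- *Post-treatment draw.* If the last dose and the end-of-treatment draw fall on day 336, the 6-week visit (±7 days) falls on days 336 + 35 = 371 to 336 + 49 = 385. A draw on days 371 to 378 lands in the Week 48 window and replaces the on-treatment value. SAP 6.1 does not exclude it.

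**4. From visit counts to patients ever affected.** With *k* boys at a grade at each of 20 visits and *N* = 96 (the planned maximum, assuming all attend), the number ever at that grade lies between *k* and min(*N*, 20*k*).

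- *k* = 1: from 1 boy (1/96 = 1.0%) to 20 boys (20/96 = 20.8%).
- *k* = 5: from 5 boys (5.2%) to 96 boys (100%, since 20 × 5 = 100 exceeds 96).

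The by-visit tables are the same at both ends of each range.

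**5. What the other outputs cover.**

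- Table 2 covers bilirubin, GGT, ALT, ACTH with cortisol, cystatin C, creatinine, BUN, urine protein and blood, and electrolytes. It pools Grades 3 and 4 for electrolytes. The SAP does not say whether its summary counts patients or values, or whether it uses all values or windowed ones. Hematology, glucose and lipids are outside it.
- SAP 5.7.1 counts subjects with laboratory abnormalities reported as treatment-emergent adverse events. Under protocol 8.1.1, abnormalities that need neither intervention nor further investigation are not reported as adverse events.
- By-patient listings (SAP 5.1) hold the values but are not a summary.

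**6. Can the overwriting be sized?** Suppose, purely as assumptions, a 1% chance of a high grade at each of 20 independent visits, with a share *q* of such values overwritten. Boys ever high-grade: 96 × (1 − 0.99^20) = 17.5. Boys visible somewhere in the shift tables: 96 × (1 − (1 − 0.01(1 − *q*))^20), which is 17.5 at *q* = 0, 9.2 at *q* = 50% and 0 at *q* = 100%. Nothing in the documents narrows *q*, so the result spans the whole scale and is not an estimate.

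**The case against.** The strongest reply is that little is really hidden. Protocol 8.1.1 makes an abnormality that needs intervention or investigation beyond a repeat test an adverse event, unless it belongs to a clinical event already reported. Protocol 8.5 asks for the highest grade of each episode, and SAP 5.7.1 counts subjects. Abnormalities that were acted on are therefore the least likely to go unseen. Repeats are prescribed mainly for the parameters in protocol Table 3, which SAP Table 2 summarises separately. Confirmation may also wait for the next scheduled visit, which normally falls in the next window and overwrites nothing.

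This stands, and it rules out two inferences that a reader might draw: that laboratory severity and per-patient frequency are lost altogether, and that resolved high grades vanish from the report. By-visit grades, Table 2 tiers, adverse-event counts and listings remain. Nor do the documents support any percentage for the understatement.

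Two further points are fair. A worst-grade table for AST would largely show the disease, since protocol 13.2.3.1.2 describes values 10 to 20 times the upper limit from muscle breakdown. The lipid concern in protocol 13.2.3.4 is about means that rose and then stabilised, which by-visit summaries can follow. Neither assay is a strong example.

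It may also be said that the SAP's sentence on parameters without a CTCAE scale takes in adrenal and urine tests. It names neither and follows a sentence limited to hematology and biochemistry. If that was the intention, the SAP should say so.

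The reply does not reach the main gap: no retained output gives, for every relevant assay, the number of patients by worst grade.

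**Conclusion.** The point holds as an undeclared omission from the primary safety reporting. The worst-grade table is absent, the adrenal and urine shift tables are not carried over, and SAP 7 mentions neither. The retained shift tables cannot recover per-patient frequency: for a constant one in 96 per visit the true count may be anywhere from 1 to 20 boys. They can also hide a high grade when a later, lower value falls in the same window.

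The gap is clearest for assays outside Table 2 and for abnormalities that do not qualify as adverse events. For Table 2 parameters it depends on a counting rule that the SAP does not give. The amount hidden by overwriting cannot be estimated from the documents, and it is zero where no later value falls in the window.

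A reader might also infer that the by-visit shift tables must use the worst value in each window. The protocol asks for shifts from baseline to each visit and sets no such rule. The last-value rule is acceptable there once the worst-grade table is present.

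The ranges assume 96 boys with a value at all 20 visits. The verdict on the omission needs no assumption.

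**What to change.** In SAP 5.7.2:

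- Restore the table of worst post-baseline CTCAE grade per patient and assay, each patient counted once, with the shift from his baseline grade. Use all scheduled and unscheduled values, including those on days 2 to 41, from first dose to the end of a defined on-treatment period. The treatment-emergent period in SAP 5.7.1 is one candidate. Say whether the post-treatment draw counts.
- Restore the adrenal and urine shift tables.
- State that the Table 2 summary counts each patient once per parameter and uses all values, not windowed ones.

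In SAP 7, list any of these departures that is intended, with the reason.

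The cost is SAP wording and one extra set of tables from data already collected. Reported abnormality counts are likely to be somewhat less favourable, and for assays driven by muscle breakdown the table will need a note that high grades reflect the disease.

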5.7.3 Vital Signs

Vital signs (systolic and diastolic blood pressure, pulse rate, body weight, height, ulna length, arm span, and body temperature) will be summarized by visit for overall subjects.

Number (%) of subjects with meeting hypertension criteria as the following will be summarized.

- If age <18 years old, the hypertension criteria are based on age, gender, and height-adjusted systolic blood pressure (SBP) and diastolic blood pressure (DBP) percentile results [USDHHS 2005] (Hypertensive: ≥95th percentile; Pre-hypertensive: 90 - <95th percentile; Normal: <90th percentile).
- If age ≥18 years old, hypertensive: SBP ≥140 mmHg or DBP ≥90 mmHg; pre-hypertensive: SBP 120 - 139 mmHg or DBP 80 - 89 mmHg; Normal: SBP 90 -119 mmHg and DBP 60 - 79 mmHg.

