7.2.7. Height/Ulna Length/Arm Span

Height (in cm) will be measured at Screening (Visit 1), at Week 24 (Visit 4), Week 48 (Visit 6), and Week 72 (Visit 8), Week 96 (Visit 10), Week 120 (Visit 12), Week 144, Week 168 (Visit 16), Week 192 (Visit 18), Week 216 (Visit 20) and Week 240 (Visit 22 End-of-Treatment/Premature Discontinuation) in ambulatory patients.

For nonambulatory patients, due to the difficulty in obtaining an accurate standing height measurement, ulna length and arm span will be used, as a surrogate measure for height (see Study Manual). Ulna length and arm span (in cm) will be measured at Screening (Visit 1), Week

24 (Visit 4), Week 48 (Visit 6), and Week 72 (Visit 8), Week 96 (Visit 10), Week 120 (Visit 12), Week 144, Week 168 (Visit 16), Week 192 (Visit 18), Week 216 (Visit 20) and Week 240 (Visit 22 End-of-Treatment/Premature Discontinuation).

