10.4.5.3. Physical Findings

Physical findings (weight, physical examination data, systolic and diastolic blood pressure, radial pulse rate, and body temperature) will be listed and summarized by visit. Where appropriate, changes from baseline at each visit will be summarized and tested using the paired t-test or a nonparametric alternative.

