13.2.3.5 Blood Pressure Assessment

During the Phase 2b double-blind study of ataluren in nmDMD (PTC124-GD-007-DMD), 6 patients – all receiving corticosteroids – had hypertension (or increased blood pressure) reported as adverse events (0 for ataluren 20, 20, 40 mg/kg, 5 for ataluren 10, 10, 20 mg/kg, and 1 for placebo). For this reason, blood pressure will be monitored via standardized procedures at each visit.

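### SAP 5.7.3 counts hypertensive subjects without reference to baseline, leaves out the protocol's change from baseline in blood pressure without declaring it, and uses adult categories with a gap and an overlap

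*SAP*

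**What the plan says.** **Protocol.** Section 10.3 lists the statistics for continuous variables and adds that changes from baseline get the same summary. Section 10.4.5.3, which covers blood pressure, says: "Where appropriate, changes from baseline at each visit will be summarized and tested using the paired t-test or a nonparametric alternative". Section 13.2.3.5 explains the interest: in Study 007 six patients, all on corticosteroids, "had hypertension (or increased blood pressure) reported as adverse events". It gives this as the reason for measuring blood pressure in a standardized way at each visit.

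**SAP.** Section 5.7.3 covers blood pressure, pulse and "body weight, height, ulna length, arm span, and body temperature) will be summarized by visit for overall subjects". It then asks for the number and percentage of subjects meeting hypertension criteria. Under 18, "the hypertension criteria are based on age, gender, and height-adjusted systolic blood pressure (SBP) and diastolic blood pressure (DBP) percentile results", with bands at the 90th and 95th percentiles. For adults: "If age ≥18 years old, hypertensive: SBP ≥140 mmHg or DBP ≥90 mmHg"; pre-hypertensive is SBP 120-139 or DBP 80-89; normal is SBP 90-119 and DBP 60-79. No baseline shift and no change from baseline are mentioned. SAP section 7 reports the paired t-test as removed for the walk test, timed tests, NSAA, EK and spirometry. Vital signs are not in that list.

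**Height.** Protocol 7.2.7 schedules height at Screening and every 24 weeks, ending with "Week 216 (Visit 20) and Week 240 (Visit 22 End-of-Treatment/Premature Discontinuation) in ambulatory patients". On the same visits, "For nonambulatory patients, due to the difficulty in obtaining an accurate standing height measurement, ulna length and arm span will be used" as the substitute, with details left to the Study Manual.

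**The concern.** Safety is the primary endpoint, there is no concurrent control, and blood pressure is one of the findings for which the protocol sets out specific monitoring. Protocol 6.4.5 says that ataluren given with systemic corticosteroids may raise the frequency of hypertension, and that the data so far do not settle ataluren's part in it. Each subject's own baseline is the only reference the study has.

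Some subjects may already be hypertensive at entry. No exclusion criterion in Protocol 4.3 names hypertension; only the general criterion on uncontrolled conditions, at the investigator's discretion, could touch it. A count of subjects meeting criteria then mixes those who arrived hypertensive with those who became so. Without change from baseline, the continuous summaries do not fill the gap: by-visit means also move as subjects leave the study.

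**Working it through.** The plan states no figure on this point to reproduce. The check sets the passages side by side and adds some simple arithmetic.

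**1. Is the change from baseline really gone?**
- Protocol 10.3: change from baseline for continuous variables in general. SAP 5.1 gives the same list of statistics without that sentence.
- Protocol 10.4.5.3: change from baseline for blood pressure, where appropriate. SAP 5.7.3: by-visit summary only.
- SAP 5.7.2 states change from baseline for continuous laboratory parameters, and SAP 5.8.7 states it for LVEF. Where the SAP wants it, it says so.
- SAP section 7 declares neither the loss of the blood pressure change summary nor the loss of its test.

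**2. What does the count identify?** Let V be the number meeting criteria on treatment, of whom P already met them at baseline and I = V - P are new.
- If only V is shown, I can lie anywhere from 0 to V.
- Suppose the count is shown by visit including baseline, which the text permits but does not state. Then B (the number at baseline) is known too. With n subjects classified at both times, I lies between max(0, V - B) and min(V, n - B). The two margins still do not fix the number of new cases.
- A shift table gives I directly.

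**3. Adult categories, tested on two readings.**
- 105/55: SBP is below 120 and DBP below 80, so it is neither hypertensive nor pre-hypertensive. Normal needs DBP 60-79, and 55 fails. Result: no category.
- 145/85: SBP is at least 140, so hypertensive. DBP lies in 80-89, so also pre-hypertensive. Result: two categories, with no order of precedence given.
- The hypertensive count itself is right in both cases. The pre-hypertensive and normal counts are not, and a shift table built on them would lose or double-count subjects.

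**4. The signal the protocol raises.** Counts are from Protocol 13.2.3.5 and arm sizes from Protocol 2.2.3.2.2:
- low dose (the dose used here): 5/57 = 8.8%
- placebo: 1/57 = 1.8%
- high dose: 0/60 = 0%
- low dose against placebo, two-sided Fisher exact test: p = 0.21

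This is a reason to look, not evidence of an effect.

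**5. Height for the percentile.** Blood pressure is scheduled at Screening, Week 1, every 12 weeks to Week 240 and Post-Treatment: 1 + 1 + 20 + 1 = 23 visits (Protocol 7.2.5). Height or its substitute is scheduled at Screening and every 24 weeks to Week 240: 1 + 10 = 11 visits. So 23 - 11 = 12 blood pressure visits have no same-visit height for any minor. The SAP does not say which height applies there, or which substitute and conversion serve nonambulatory minors. For spirometry it does choose: SAP 5.8.5 uses ulna length.

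**The case against.** **The signal is covered elsewhere.** The Study 007 cases were adverse events. Here TEAEs are tabulated by SOC and PT, and SAP 5.7.1 adds a count of abnormal vital signs reported as TEAEs. By definition a TEAE begins or worsens after the first dose, so that route does separate new from old. This stands in part. Protocol 8.1.1 makes an abnormal physiological finding reportable when it needs intervention or investigation beyond a repeat test, so a raised reading that prompts no action need not appear. Protocol 13.2.3.5 answers the signal with measured blood pressure, and SAP 5.7.3 holds the only classification of it.

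**Silence is not a conflict.** The SAP overrides the protocol only where the two conflict, the protocol says where appropriate, and SAP 6.3 defines change from baseline in general. So the protocol's summary may still be owed. That is fair, but a definition is not an instruction to produce a table, and one line would settle it.

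**The table is descriptive.** The study tests no formal hypothesis, and individual readings will be in the listings. This stands and limits the severity.

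**A stronger reading to avoid.** A reader might infer that nonambulatory minors cannot be classified at all, because height is measured only in ambulatory patients. The documents do not support that. SAP 5.7.3 asks for height adjustment, not standing height. Protocol 7.2.7 collects ulna length and arm span at the same visits as a stand-in for height, and the Study Manual, not available here, may give the conversion. Subjects aged 18 or over need no height. Nor can an undercount be put in figures: the documents give neither the nonambulatory share of minors nor the denominator.

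**Conclusion.** The point holds as a gap in a descriptive safety table, of low to moderate severity. As written, SAP 5.7.3 cannot separate hypertension present at entry from hypertension that appears on study. It also omits the protocol's change from baseline in SBP and DBP without declaring it. The adult categories are neither exhaustive nor exclusive, which affects the pre-hypertensive and normal counts but not the hypertensive count. The height source is a matter of missing detail, not of missing data.

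This rests on two assumptions: that the table shells, which were not available, add no shift or change summary beyond the SAP text, and that some subjects may be hypertensive at entry. The size of any distortion cannot be computed, because the documents give no baseline prevalence. Even after the fix, all subjects have had ataluren before and there is no control, so a shift would show change since entry into this study and not its cause.

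**What to change.** In SAP 5.7.3:
- Add a shift table from baseline to worst on-treatment category (normal, pre-hypertensive, hypertensive), overall and by corticosteroid use.
- Restore descriptive change from baseline in SBP and DBP by visit, or declare its removal in section 7.
- Make the adult categories exhaustive and mutually exclusive: assign the worst category met, and give readings below 90 or 60 that meet no higher category a stated place.

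As a clarification, state that height for nonambulatory minors comes from a substitute already collected under Protocol 7.2.7 (for example ulna length, as in SAP 5.8.5), and name the conversion. State also that the latest available height is carried to the 12 of 23 visits without one, and that the denominator is classifiable subjects.

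**Cost.** SAP wording and a little programming; no new data. Estimated height adds a small error to the percentile. A worst value taken over up to 20 scheduled on-treatment visits (23 less Screening, Week 1 and Post-Treatment) will pick up isolated high readings, so it should be read beside the by-visit changes.
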